**To evaluate system-level hypotheses, the design is a repeated cross-sectional study with outcomes**

measured for distinct cross-sectional samples of patients at five points. To analyze these data, we will first use chi-square tests to compare proportion of eligible patients meeting guidelines at 12 and 24 months before implementation to proportion of patients meeting guidelines 12, 24 and 36 months after system-level strategies are in place. We will then use segmented logistic regression models to identify the time point at which observed trend in proportion of patients meeting guidelines. We expect a significant p-value for change in proportion of patients meeting guidelines after implementation of system-level strategies. Conversely, we expect the trend for proportion of patients meeting care guidelines before implementation to be stable with a larger p-value. This trend, in conjunction with additional qualitative information gathered about implementation (Aim 3), will provide evidence that implemented strategies resulted in changes in outcomes.

**Power/sample size:** To demonstrate a minimum increase of 10% in the primary outcome after implementation of system-level strategies as compared to before implementation, a sample of 170 patients at each time point will provide 80% power at the 0.05 significance level based on the chi-square test for comparing proportions. We have many more patients than needed; as system-level outcomes will be evaluated using EMR data, we will include all eligible patients and conduct subgroup and sensitivity analyses to better characterize effects.

**For the patient-level hypothesis,** the design is a repeated measures study with outcomes measured on the same patients at three time points; at baseline and 6 months, and 12 months after transition to the complex care team for each individual patient. We will use linear mixed models to estimate effects on change in scores. Through specification of fixed effects, the mixed model allows for control of confounding variables, and can account for sources of natural heterogeneity by adding random effects that are unique to a particular individual. We will test different covariance matrices for random effects and will choose the matrix yielding smallest Akaike information criterion or largest restricted maximum likelihood estimate. Residual analyses and plots will examine adequacy of the final model. We will use SAS Proc Mixed procedure for analysis. Retrospective data might be missing. If data are missing at random (MAR), a linear mixed regression model is appropriate to address the issues of repeated measures and missing data in longitudinal studies. If the missing data are not missing at random (NMAR), we will explore the missing data pattern and a technique such as pattern mixture model will be used to adjust for NMAR bias.

**Power/sample size:** Assuming intra-subject correlation of 0.7 and minimum detectable standardized effect size of 0.25 (standardized effect size = effect size/standard deviation), we will need 402 patients to attain 80% power at  $\alpha=0.05$  using proposed mixed-effects linear regression analyses.

**Aim 3: (Research Component) *Conduct an intervention mixed-methods evaluation of implementation of care coordination strategies.*** This is especially important for system interventions implemented in the context of real world settings as proposed in this application to: (a) describe how the system-level strategies are implemented; (b) elucidate contextual factors affecting implementation at system and patient-levels; and (c) identify alternate explanations for observed effects on outcomes to generate counterfactual inference. Gathering qualitative and quantitative data before, during, and after implementation will enable us to assess the factors that influence implementation at system- and patient levels. Data collection methods include structured observations, complex care team surveys and provider interviews, patient surveys and interviews, and EMR extraction.

**Structured observations** - quiet observation of daily clinical work with opportunistic discussion with staff at the primary care clinics, Patient Access Center, and the complex care team- will describe usual care prior to and document how workflow changes after strategies are implemented. Adapted from anthropological participant observation, this method lends itself to multiple levels of observation and analysis. Led by [name], research staff will conduct 40 hours of structured observation prior to implementation and at 3 and 6 months post-implementation.

**Patient surveys and interviews** will assess experience of care coordination and its broader effects on health-related quality of life as well as the mediating and/or moderating effects of patient activation, attitudes toward follow-up cancer care, care quality, challenges of daily living (multiple low-wage jobs), competing demands/structural barriers to access (transportation, no paid time off), and health literacy. Administration of patient surveys is described in Aim 2 above. We will stratify across the two cancer types compared to a usual care sample of complex patients without cancer, and account for originating clinic. Interviewing across these groups will elucidate the experience of coordination for patients with multiple chronic conditions and enable us to see how cancer may create additional or different needs or perceptions. Additional patient interviews will be conducted to assess receipt of a care plan, survivor-level outcomes, experience with survivorship, and to understand the impact of COVID-19. These interviews will allow us to understand the patient experience throughout the cancer care continuum.

**Interviewing providers and focus groups** from primary clinics with high and low rates of survivors' referred to the complex care team will help identify "work-arounds" and protocols that impede or facilitate care coordination, e.g. primary and specialty physician communication. Providers (n=30), sampled based on their involvement in cancer survivor follow-up care and chronic disease management, will be invited to interviews which will assess perspectives on patient uptake and other perceived challenges and opportunities. The PIs will develop interview guides, train and supervise the team in conducting interviews. Focus groups (N=2) and additional provider interviews (N=10) will be conducted to understand provider perceptions and experience treating cardiovascular disease risk for cancer survivors.

**Epic EMR data Extraction will be used to characterize:** (1) visit patterns with the nurse coordinator; (2) the extent to which care coordination, disease management and referrals to specialty providers and receipt of referrals occur; (3) patients who do not receive appropriate follow-up services; (4) missed appointments or loss-to-follow-up; and (5) processes related to care coordination. A separate data extraction of 1000 non-cancer patients with multiple chronic conditions will allow us to analytically characterize the non-cancer comorbid patient population at baseline as a comparator. We will also recruit a small subsample of these for baseline pre-intervention surveys and interviews.

**Aim 3 Data analyses:** We will use NVivo 9.0 (QSR International, AUS) to collate and analyze qualitative data. Use of this software makes the analytic process transparent so that investigators can track evolving analyses. Research staff will transcribe field notes from structured observations and gather existing protocols and documents relating to care of complex patients to enter into the database. We will develop flowcharts depicting complex care and primary care team members' relationships, roles, responsibilities, and behaviors in relation to practice change. Drs. [name] and [name] will work with research staff to organize these source documents and develop a codebook relating data to practice change, behavioral and organizational theories. We will triangulate across diverse data sources, to understand how providers adapt the strategies to suit the Parkland

context. Through monthly meetings, we will test emergent themes and interpretation against the knowledge base of our study team. We will review coding agreement and resolve discrepancies through consensus. Cross-analysis of qualitative data from all sources will enable integration across strategies and implementation processes to assess key steps and the interface of oncology and primary care. Using waves of surveys from Aim 1, we will explore whether changes in teamwork scores correlates with changes in primary outcomes in Aim 2.

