### 3. Study Procedures:

We expect approximately 1000 new survivors with  $\geq 1$  prevalent chronic condition to be eligible. We will not include patients diagnosed with *in situ* and metastatic disease (Stages 0 and IV) due to insufficient evidence for routine follow-up and management; many of the latter continue indefinitely on active treatment for symptom management. The chronic conditions we selected for inclusion are the most prevalent conditions cancer survivors have at Parkland as well as nationally.

**Aim 1: (Quality assurance/quality improvement) Parkland will implement system-level EMR-driven evidence-based care coordination strategies; (1) EMR-driven registry to facilitate patient transitions between primary care and oncology care, (2) co-locate a nurse practitioner trained in care coordination within a complex care team, and (3) enhance teamwork through coaching and technical assistance.**

- **Strategy 1:** Using the Epic Reporting Workbench, Parkland EMR data will be extracted in order to create a registry of complex cancer patients to facilitate transitions primary care and oncology care.
- **Strategy 2:** During Year 1 of this study, Parkland will educate clinicians and staff about the proposed system change and train primary care physicians on ways to identify and refer survivors to the complex care team. Parkland will designate a new complex care team for

eligible patients. This team will be housed within a Parkland community oriented primary care clinic. Due to the acuity and complexity of the needs of complex cancer survivors, the team will be staffed by a primary care physician and a nurse practitioner, and will include an RN/LVN nurse, a medical assistant, a social worker, and a mental health counselor.

- **Strategy 3:** Parkland will map team workflow around all aspects of delivering care to complex cancer survivors, establishing team goals, train team members in all aspects of cancer survivorship care including providing booster training sessions and coaching, enhance communication, set ground rules to make decisions, and finally pro-actively create standing orders to empower non-physician team members to share care delivery. Parkland will facilitate primary care teams in developing systems needed to enhance teamwork and implementing incremental practice change initiatives through quality improvement cycles.

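### The segmented logistic model is given the task of locating the change and its break is not fixed at implementation; an unadjusted search would give about 8% to 16% false positives, and the trend-adjusted test has little power even with a fixed break

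*Combined protocol and SAP*

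**What the plan says.** Section 3 (Study Procedures), Aim 2, describes the system-level outcomes as "measured for distinct cross-sectional samples of patients at five points". The analysis has two steps.

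- Step 1: "we will first use chi-square tests to compare proportion of eligible patients meeting guidelines" at 12 and 24 months before implementation with the "proportion of patients meeting guidelines 12, 24 and 36 months after system-level strategies are in place".
- Step 2: "We will then use segmented logistic regression models to identify the time point at which observed trend in proportion of patients meeting guidelines". The sentence has no verb for the trend.

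Two expected results follow: "We expect a significant p-value for change in proportion of patients meeting guidelines after implementation of system-level strategies", and "we expect the trend for proportion of patients meeting care guidelines before implementation to be stable with a larger p-value". The plan then says that this trend, read together with the Aim 3 qualitative findings, will be the evidence that the strategies changed outcomes. The opening line of the Aim 2 statistical analyses names segmented logistic regression, not the chi-square test, among the methods for judging the strategies' effect.

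The plan gives no model equation, break date, list of candidate breaks or cut-off for a searched break. The 170 patients per time point and 80% power are stated for the chi-square test. No event is named as time zero. Under Aim 1, Strategy 2, "During Year 1 of this study, Parkland will educate clinicians and staff about the proposed system change", and the same strategy also sets up a new care team, so more than one date could qualify.

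**The concern.** The start of the strategies is a design constant, so the natural question is whether level or slope changes at that date. A model asked to find the time point answers a different question. Taking the best-fitting of several breaks and reading its p-value as if it had been fixed in advance makes that p-value too small. The selected break may also fall before implementation or between months 24 and 36, and the plan does not say how such a result would be read.

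This matters because there is no concurrent control for the system-level outcome. A before/after chi-square test cannot separate an effect of the strategies from a drift that was already under way. Only the segmented model can attempt that, and it is the part left unspecified.

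**Working it through.** **Inputs.** Times are -2, -1, +1, +2 and +3 years from implementation, with 170 patients per point, a 10-point increase and alpha 0.05 (Aim 2). Assumptions: two-sided testing, equal numbers per point, independent patients, and a 43% baseline. The 43% is the Background section's figure for colorectal survivors meeting both surveillance and diabetes guidelines. It is not a rate for the primary outcome, so baselines of 20% to 60% were also tried.

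**Reproducing the plan's 170.** Pool two pre points against three post points (ratio r = 1.5), with p1 = 0.43, p2 = 0.53 and mean (0.43 + 1.5 × 0.53)/2.5 = 0.49:

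n_pre = [1.96·√((1 + 1/1.5) × 0.49 × 0.51) + 0.8416·√(0.43 × 0.57 + 0.53 × 0.47/1.5)]² / 0.10² = (1.265 + 0.540)²/0.01 ≈ 326

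That is 163 per point. With continuity correction it is 343, or 172 per point. Power at 170 per point is 81.7% uncorrected. So 170 is reproduced as a pooled before/after comparison. One point against one point at 170 each has only 45% power.

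**False positives when the break is searched.** Constant rate, grouped logistic models, likelihood-ratio test, 40,000 simulated data sets per setting. The largest statistic over the candidate breaks is compared with the ordinary 1-df cut-off of 3.84.

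| Model and candidates | False-positive rate |
|---|---|
| Break fixed at implementation, any model tried | 4.8% to 5.4% |
| Step only, four gaps | 15.3% |
| Step plus linear trend, four gaps | 16.0% |
| Slope-change join point | about 12% |
| Searches requiring at least two points on each side | 8.2% to 9.4% |

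The searched rates are 8.2/5 = 1.6 to 16.0/5 = 3.2 times nominal. They barely move with baselines of 20% to 60%, or with 200 per point. To hold 5%, the cut-off would have to rise from 3.84 to about 4.7 to 6.1.

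**Placement of a true step from 43% to 53% at implementation, 170 per point.**

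| Model and candidates | Correct interval or date |
|---|---|
| Step only, four gaps | 77% |
| Step only, at least two points each side | 88% |
| Step plus trend, four gaps | 37% |
| Step plus trend, at least two points each side | 63% |
| Level plus slope change, two candidates | 57% |
| Slope-change join point | 8% |

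If the rise is gradual, reaching 10 points by month 36, the step-only search places the break at implementation in 29%.

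**Power with the break fixed.** The log odds ratio is ln(0.53/0.47) - ln(0.43/0.57) = 0.402. The information per point is 170 × 0.43 × 0.57 = 41.7 before and 170 × 0.53 × 0.47 = 42.3 after.

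- Step only: SE = √(1/(2 × 41.7) + 1/(3 × 42.3)) = 0.141; z = 0.402/0.141 = 2.85; power = Φ(2.85 - 1.96) ≈ 81% (82% by simulation).
- Step plus trend: the step indicator (0, 0, 1, 1, 1) and time have sums of squares 1.2 and 17.2 and cross-product 4.2, so r² = 4.2²/(1.2 × 17.2) = 0.855. Only about 14.5% of the information on the step remains. SE = 0.369, z = 1.09, power ≈ 19%. Simulated power is 20% to 21% at baselines of 30%, 50% and 60%, and 26% at 20%.
- Level plus slope change: 15% for the joint 2-df test and 16% for the level term alone. With two pre points the pre-implementation line is fitted exactly, with nothing left to check it.

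**The case against.** The strongest reply is that the sentence is unfinished and its neighbours speak of change after, and stability before, implementation. On that reading the authors intended an ordinary interrupted time series with the break at implementation. That reading is reasonable, and no search procedure or unadjusted cut-off is written anywhere. But the neighbouring sentences state expected results and do not constrain the model, so an analyst who searched for the break would still comply with the text.

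Three stronger readings are tempting, and the documents do not support them.

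- A reader might infer that the plan replaces a test at implementation with a search. It does not: the chi-square step splits at that date, carries the power statement, and is untouched by any search.
- A reader might infer that the error rate is bound to double or triple. That requires an unadjusted cut-off, which the plan neither states nor excludes, and the rate is only about 8% to 9% if each side must hold two points.
- A reader might infer that the change would usually be misplaced. That is false for a step-only model with an abrupt step. It is true for step plus trend over four gaps, for slope join points, and for a step-only model when the rise is gradual.

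It is also fair to object that fixing the break does not rescue the model, because its power is then very low. That stands, and it has to be stated alongside the fix.

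**Conclusion.** The point holds in a limited form. The plan assigns the segmented model to finding a time point, does not fix its break at implementation, and rests part of its effect claim on that model. If the break is searched without adjustment, the false-positive rate is about 8% to 16% instead of 5%. This result does not depend materially on the assumed baseline. The placement and power figures rest on an abrupt 10-point step, a 43% baseline, 170 independent patients per point and two-sided testing. Separately, the stated 80% power does not carry over to the segmented model: a trend-adjusted test has about 15% to 20% power under those assumptions, so a non-significant result there says little about whether the strategies worked.

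**What to change.** Replace the incomplete sentence with something like: *The segmented logistic model has its break fixed at one implementation date, defined by a named event before outcome data are examined; the change in level and slope is estimated and tested at that date.* The sponsor should choose the event, since staff education and the start of the care team may fall on different dates.

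Keep any data-driven break search as a sensitivity analysis only, with a permutation or sup-type reference distribution.

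Add to the power paragraph that 80% applies to the chi-square comparison alone, that the trend-adjusted segmented test has about 15% to 20% power for a 10-point step at 170 per point, and that a non-significant result from it will not be read as no effect.

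The cost is one or two sentences on the model and a line on power, with no new data. The downside is a visibly less favourable stated power for the segmented model.

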**Patient-level hypothesis:** **Patient-reported care coordination assessed via Patient Perception of Care Scale**, which has been validated in primary care and is associated with improvements in reported problems with care coordination. We will use the EMR-generated registry to randomly select 866 complex cancer survivors to survey 402. Surveys will be administered three times by phone – once prior to their initial visit with the complex care team (baseline) and twice thereafter at 6 and 12 months. Prior to fielding surveys, we will conduct 15 cognitive interviews (with patients who will be excluded from the larger project) to ensure measures not already validated in Spanish are adapted for language, literacy and culture.

**Aim 2 Statistical analyses:** We will use segmented logistic regression and linear mixed regression models to assess effect of care coordination strategies on system and patient outcomes.

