#### **6. Sources of Research Material:**

Data for this study will include:

- 1) Electronic Health Record (patient demographics, cancer and comorbidity diagnoses, appointments and dates, lab results and dates, screening procedures including results and dates, smoking history, medications, cancer treatment data). For the retrospective component of the study, we will request the EMR data from 01/01/2010- 12/31/2016. An additional sample of patients without cancer, but with 2 or more chronic conditions and a doctor visit in the last 12 months as a comparator group.
- 2) Patient survey data about patient experiences of care - validated measures
- 3) Audio-recordings of patient and provider interviews will collect qualitative data about patient experiences of care
- 4) Field notes of structured observations of clinic workflow

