#### **7. Recruitment Methods and Consenting Process:**

**To evaluate the system-level outcome,** we will use EMR data collected on approximately 1000 patients from the Parkland system. We will ask the IRB for Waiver of Consent and Waiver of HIPAA

Authorization for EMR review and extraction of outcome data, and to conduct a confirmatory audit of 50 patient records identified by the EMR algorithm for individual chart review to confirm our ability to accurately capture all complex, Stage I-III breast, colorectal cancer patients completing active treatment.

**To evaluate the patient-level outcome**, we will use the EMR-generated patient list to randomly select ~866 complex cancer survivors in order to survey at least 402 after their transition to the complex care team. Based on our prior research experience with contacting Parkland cancer patients, patients are able and willing to complete telephone surveys. Further, we can expect 55% of those eligible will participate (n~480); 12% will actively refuse, 13% will have a non-working number, and 20% will be unreachable. We will also request a Waiver of HIPAA Authorization to identify and invite patients, and to compare, subsequently, demographics of non-respondents with participants to examine selection bias. All patients included in the system-level and patient-level outcomes are Parkland patients of the study investigators.

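### A non-significant trend over two pre-implementation points is read as stability, but that check has about 8% power against a drift that alone would give the 10-point target difference

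*Combined protocol and SAP*

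**What the plan says.** Section 3 (Aim 2, system-level hypotheses) describes independent cross-sections at five points: 24 and 12 months before implementation, and 12, 24 and 36 months after. Chi-square tests come first. The next step reads: "We will then use segmented logistic regression models to identify the time point at which observed trend in proportion of patients meeting guidelines". That sentence is unfinished, so the purpose of the segmented model is not fully stated.

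The plan expects a significant p-value for the change after implementation. Of the earlier period it says: "Conversely, we expect the trend for proportion of patients meeting care guidelines before implementation to be stable with a larger p-value". The conclusion follows directly: "This trend, in conjunction with additional qualitative information gathered about implementation (Aim 3), will provide evidence that implemented strategies resulted in changes in outcomes".

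The opening line of the Aim 2 analysis text gives the segmented model a larger role: "We will use segmented logistic regression and linear mixed regression models to assess effect of care coordination strategies on system and patient outcomes". The sample-size paragraph, however, rests on a chi-square test for a 10% increase: "a sample of 170 patients at each time point will provide 80% power at the 0.05 significance level". It gives neither the baseline proportion nor the grouping of time points.

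The plan states no tolerable pre-implementation drift, no confidence interval for the slope and no power for the trend check. The 1,000 non-cancer patients (Section 3, Aim 3, EMR extraction) are characterised at baseline only, so they provide no concurrent trend.

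**The concern.** A large p-value shows stability only if the test could have detected a drift that matters. Two points of about 170 patients give a very imprecise slope, so non-significance is the likely result whether or not care was already improving.

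What follows depends on which test carries the effect claim, and the plan does not settle this.

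- **Before/after chi-square plus a quiet pre-trend.** A steady secular improvement can produce exactly this pattern with no effect of the strategies.
- **Segmented level-change term.** The model adjusts for a linear trend and so protects against that error. The stated 80% power does not describe it, and its real power is far lower.

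At stake is whether a change in the primary system-level outcome can be attributed to the strategies at all.

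**Working it through.** **Inputs.** Times in years are −2, −1, +1, +2, +3; 170 patients per point; α = 0.05 (two-sided assumed); target 10 points (read as absolute), all from Section 3. The baseline is an assumption: 43%, the Section 2 figure for colorectal survivors meeting both surveillance and diabetes-care guidelines. Baselines of 20–60% were also run.

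**1. The plan's own figure.** Pooling the two pre-points (340) against the three post-points (510), 43% versus 53%, gives 81.7% power, in line with the stated 80%. A single 170 versus 170 comparison gives 45%. The stated figure therefore fits a pooled chi-square at a mid-range baseline, with no secular trend.

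**2. Drift equivalent to the target.** Mean pre time is −1.5 and mean post time +2, a gap of 3.5 years. 10 / 3.5 = 2.86 points per year.

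**3. Precision of the two-point pre-slope.**
- SE = √(2 × 0.43 × 0.57 / 170) = 0.0537, or 5.37 points per year.
- 95% half-width = 1.96 × 5.37 = 10.5 points per year (8.5–10.5 over baselines 20–60%).
- Drift detectable with 80% power = 2.80 × 5.37 = 15.0 points per year (12–15).
- Power at 2.86: 2.86 / 5.37 = 0.532; Φ(0.532 − 1.96) + Φ(−0.532 − 1.96) = 0.077 + 0.006 = 8.3% (8–10% over the same baselines).

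Larger cross-sections help little: at a 43% baseline, 200 per point gives 8.9% and 1,000 per point about 25%. About 4,750 per point would be needed for 80%.

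**4. How often pure drift produces the hoped-for pattern.** Binomial simulation (150,000 runs, linear drift, no effect of the strategies, pre-period mean 43%). The pattern is a significantly positive pooled chi-square with a non-significant pre-trend.

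| Drift (points/year) | Pattern seen, 43% baseline | 20% baseline | 60% baseline |
|---|---|---|---|
| 2.86 | 75% | 82% | 78% |
| 2 | 49% | 60% | 51% |
| 1.5 | 31% | 40% | 32% |
| 1 | 16% | 21% | 17% |
| 0.5 | 7% | 8% | 7% |

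With no drift the reference value is 0.025 × 0.95 ≈ 2.4%. If only −12 and +12 months are compared, the 2.86 case falls to 17%.

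**5. Segmented model, break fixed at implementation.** Under drift of 2.86, simulated two-sided rejection for the level change is 5.2% with separate slopes and 5.0% with a common slope. Power for a true step from 43% to 53% is 16% and 19% respectively. A linear approximation shows why. With separate slopes, the variance of the step at time 0 is σ² × [(1/2 + 1.5²/0.5) + (1/3 + 2²/2)] = 7.33σ², with σ² = 0.2451/170. The SE is then 10.3 points, about the size of the step itself.

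**6. What a longer pre-series buys.** Section 7 says "we will use EMR data collected on approximately 1000 patients from the Parkland system". Assume that this total covers all points, split evenly, with three post-points and annual pre-points. Pre-slope SE = √(0.2451 / (n × Sxx)), with Sxx = 0.5, 2, 10 and 28 for two, three, five and seven pre-points.

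| Pre-points (n each) | Pre-slope half-width (points/year) | Power to see 2.86 points/year | Segmented power, 10-point step |
|---|---|---|---|
| 2 (200) | 9.7 | 9% | 18–22% |
| 3 (167) | 5.3 | 18% | 22% |
| 5 (125) | 2.7 | 53% | 23–28% |
| 7 (100) | 1.8 | 86% | 21–34% |

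**The case against.** **The drift is hypothetical.** The 2.9 points per year was solved for, not observed, and the documents give no rate. At 0.5 points per year the false pattern appears in only 7% of trials. This stands as a limit on the size of the claim. It does not rescue the check, because two points cannot tell a drift of 0.5 from one of 2.9.

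**The segmented model may be the effect analysis.** The opening line of the Aim 2 analysis text supports that reading, and false attribution is then about 5%. This also stands, but the stated power does not apply to that model. The 5% and 16–19% assume a fixed break, whereas the unfinished sentence could mean an estimated one. Training in Year 1 and incremental improvement cycles also make the onset arguable, which is a reason to state the break beforehand.

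**Stability is only an expectation, and Aim 3 is there to help.** No formal p-value rule is set, and Aim 3 will "identify alternate explanations for observed effects on outcomes to generate counterfactual inference". Even so, the plan's next sentence uses the trend as evidence. Observations and interviews may suggest causes of a drift but do not estimate its size.

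**The 80% can be reproduced.** It can, by pooling. What remains there is an unstated baseline and grouping, a matter of clarity.

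**The number of usable earlier years is unknown.** No implementation date is given, so seven pre-points cannot be assured. Excluding the cognitive interviewees diagnosed in 2014 or earlier removes only 15 people and does not close the 2010–2016 window.

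**Conclusion.** The concern holds. Two pre-implementation points cannot support a claim of stability through non-significance: at 170 per point and a 43% baseline, drifts within about ±10.5 points per year of the estimated slope remain compatible with the data. The consequence for attribution is conditional. It is serious if the pooled chi-square carries the claim and care was already improving by 1 point per year or more (16% false pattern at 1, 75% at 2.9). It becomes a power problem if the segmented level change carries the claim (16–19%, against 80% stated for a different test).

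The figures rest on the assumed baseline, linear drift on the percentage-point scale, two-sided 5% tests and independent cross-sections. The power basis and the unfinished sentence are secondary matters of missing detail.

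**What to change.** 1. Extend the pre-implementation series using data already in scope. Section 6 says "we will request the EMR data from 01/01/2010- 12/31/2016", which allows up to seven annual points, fewer depending on the implementation date and the follow-up needed to score patients.
2. Fix the break at the implementation date in advance, and complete the unfinished sentence accordingly.
3. State which test carries the effect claim. Report the pre-implementation slope, the level change and the slope change as estimates with 95% confidence intervals, and remove the inference of stability from a larger p-value.
4. Give the baseline and grouping behind the 80%, and say that it applies to the chi-square comparison assuming no secular trend, not to the segmented model.

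The cost is extra programming on retrospective data already to be requested, plus wording. The gain is mainly in the pre-slope. At about 1,000 patients in total, the level change stays imprecise: its 95% half-width is about 17–19 points with two pre-points, 14–16 with five and 13–17 with seven. It should therefore be interpreted from its interval, not from significance.
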